D.2.4.3.8. The Center for Epidemiologic Studies Depression (CES-D) scale: This 20-item, self-report scale to identify depression in the general population covers major components of depression, with an emphasis on affective components: depressed mood; feelings of guilt and worthlessness; feelings of helplessness and hopelessness; psychomotor retardation; loss of appetite; and sleep disorder [277].

D.2.4.4. Potential confounding variables: Disease severity: We will adjust for disease severity using information on PCa stage or TNM stage, grade and histology from electronic medical records. Gleason score: The Gleason score is a sum of the predominant pattern and the second most common pattern of the Gleason grade. Gleason score ranges from 2 -10 classified as low (2-4), intermediate (5-7) or high-grade (8-10). Elixhauser comorbidity index: The Elixhauser comorbidity index is a medical record-based metric designed to predict death in longitudinal studies, with an integer score representing increasing burden of illness [278]. We will use diagnostic information from inpatient encounters in 180 days prior to the month of PCa diagnosis to adjust for comorbidity, following the method of Elixhauser et al. [167,168,] and will obtain comorbidity scores using PICARD and VA inpatient and outpatient databases. Demographic variables: We will gather baseline data on patient age, income, education, health insurance, occupation, marital status, smoking status, height, weight and family history of PCa as possible covariates in our analyses.

Study duration

We will use stratified randomized control trial to study association between value markers and objective (complications and cancer recurrence) and subjective (HRQoL, psychological wellbeing) outcomes across intervention groups, over 24 month period. We will recruit newly diagnosed localized PCa patients from UPHS (Hospital of University of Pennsylvania, Presbyterian Medical Center, and Pennsylvania Hospital), Fox Chase Cancer Center and Philadelphia Veterans Administration Medical Center (PVAMC) and randomize them to conjoint analysis intervention ($n=360$) or control group ($n=360$). Length of a Subject's participation time In study: 24 months All participants will complete self-administered surveys at baseline within 1-2 weeks after enrollment (prior to treatment initiation) and again 3,6,12 and 24 months post-enrollment. Projected Date of the Proposed Study: July 2013 to June 2016.

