size based on the observed differences in outcomes such as HRQoL (SF-36 and prostate cancer index, PCI) and cost of PCa care across groups. The primary outcome is HRQoL as measured by the SF-36 and PCI sub-scales. A change of 5 to 9 points on PCI is clinically meaningful [272]. Similarly, a difference of 7 points or more on the SF subscales is considered clinically meaningful [272, 275, 301]. Based on our prior research and that of Litwin et al [253, 272], the standard deviations for the PCI and SF-36 scales in samples of men with PCa mostly range from 8 to 14; hence standardized differences (SDs) of $7/14=0.5$ to $7/8=0.87$ will be clinically relevant. The power calculations for Aims 2-4 assume availability of 720 participants who are eligible for randomization into one of the two intervention groups. We assume a conservative intra-class correlation of 0.3 and 4 follow-up measures per subject. The sample size is adjusted to accommodate a 10% missing or dropout rate by 24 months based on rates over a similar period of time in previous studies [272, 275, 301]. We assume 80% power and two-sided level of significance of $\alpha = 0.05$. We have 80% power to detect a 1.2 point difference in PCI or SF-36 sub-scale. Within treatment type, the sample size is reduced to 60 per intervention arm. We have 80% power to detect a 3.0 point difference in sub-scale with 60 patients in each arm. Thus, we will have adequate power to detect differences between treatment groups [302]. Power for identifying utility based profiles and outcomes: We analyzed the levels of power for differences in outcomes between profiles defined by latent classes of attributes-specific utilities with a conservative allocation of subjects to each profile (25 in one vs. 10 in other profile) and less conservative allocation (35 in one profile vs. 35 in other profile) using a logistic model based comparison for a binary outcome (e.g. recovery of baseline HRQoL) with a 2-sided alpha of .0125 (Holms adjustment profiles). In the first allocation, the group difference of 0.56 yields 80% power; for the second allocation an effect size of 0.42 corresponds to power of 90. Thus, with our anticipated effect size of 0.51, we will have adequate power with $n=60$ in each group. (Adjusting for patient characteristics may reduce the effect sizes of the differences between profiles.)

Key inclusion criteria

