After obtaining informed consent, baseline data will be obtained in person prior to the initiation of treatment. Participants will meet with the research assistant to complete the computer-based conjoint analysis tasks. Patient identifiers will be removed to maintain data confidentiality. Only the PI will have access to the master files. For conjoint analysis, each participant will be asked to express his preference for attributes and attribute levels for active surveillance and five active treatments for clinically localized PCa (RP, RALP, EBRT, PT, BT) based on choice sets presented. The choices will vary based on the differing attributes of various treatments ascertained in prior work and focus groups. After pilot testing and refining the conjoint task in Phase 1, final attributes and levels will be used. Trade-offs among treatment features will be calculated in patient-specific utilities or part-worths associated with the attribute levels in the study. For other outcomes, participants will receive the following surveys via mail within 1-2 weeks after enrollment and prior to treatment initiation: SF-36, EPIC, AUA-SI, regret scale, CES-D, MAX-PC, SWD, PSQ-18, CPS, DCS and trust scale. Demographics, health and family history, clinical covariates and cancer progression data will be collected at 3, 6, 12 and 24 month follow-up. Histological tumor grade Gleason score and PSA and annual Elixhauser comorbidity score [257-258] will be obtained from the Pennsylvania Integrated Clinical and Research Database (PICARD), a UPHS, Fox-Chase Cancer Center electronic database, and PVAMC administrative and patient HER database. Retention and survey administration: During enrollment, importance of active participation will be emphasized. All participants will complete self-administered surveys at baseline within 1-2 weeks after enrollment (prior to treatment initiation) and again 3,6,12 and 24 months post-enrollment (see Appendix for copies of instruments, consent and medical chart review form). Non-respondents will be contacted via telephone after 10 days. In case of non-response due to death, cause of death will be noted and the physician investigators will determine cause of death (PCa or non-PCa related). The PCa conjoint analysis task, DCS, CPS and trust scale will be administered at baseline only, immediately after diagnosis of PCa and before treatment decision. Procedure for Data Sharing and Modification coordination: In Phase-1 on the study, data will be generated from focus group meetings that will take place on Penn campus. Focus group data will not be shared with other sites. This data will be used to generate a conjoint analysis instrument. This conjoint analysis instrument will be administered to participants in the intervention arm at all three sites during the Phase-2 of the study. The paper copies of various instruments that all participants complete will be stored at Penn campus in a secure office. In addition, clinical data obtained through chart abstraction will also be stored at Penn campus in a secure office. All electronic data bases will be pass word protected and only the study personal will have access to this data. Raw data will not be shared with other sites, only results in aggregate format with de-identified information will be made available to other sites. Each site PI will be responsible for addressing modifications. Additionally, the Penn site PI [name] will have overall responsibility of tracking all modifications. In case of a reportable event at a site, the site PI will inform Penn IRB and Penn site PI regarding the reportable events. Additionally, during Phase-1 of the study, we will conduct audio/video recording of focus group meetings.

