
The following documents are currently attached to this item:

There are no documents attached for this item.

Analysis Plan

Analytic Methods General: The statistical analysis will proceed in three stages: First, we will check the data quality and carry out descriptive analyses of demographics and key outcome variables. Next, we will assess preferences using conjoint analysis and inferential analysis. For continuous outcome variables, we will check for homogeneity of errors using spread-vs.-level plots and will consider transforming variables that either are highly skewed or have variance that depends strongly on the mean. We will use methods based on general linear model (univariate and repeated-measures ANOVA, mixed models) to analyze uncensored continuous outcomes, such as generic and prostate-specific HRQoL, psychological wellbeing and satisfaction with care. For potentially censored outcome variables such as time to PSA recurrence, we will use Kaplan-Meier curves and Cox proportional hazard models. Poisson regression (zero-inflated) will be used for count data. We will use Bonferroni correction for multiple testing. We will use propensity-score and instrumental variable approach to minimize observed and unobserved bias within groups (i.e. intervention group and usual care control group). **Missing Data:** We will attempt to prevent missing data by ensuring that data collection is as complete as possible. Should there be substantial missing data, however, we will employ analysis and imputation methods to reduce bias and increase efficiency [279-282]. Based on the proportion of missing data, we will use complete-case analysis, or explore available techniques, such as standardized score imputation, simple means imputation, maximum likelihood model-based imputation, data augmentation, etc. [281]. When data are evidently non-missing at random, we will conduct explicit non-ignorable modeling and sensitivity analysis [278]. **Propensity score matching:** In observational studies, comparisons between treatment groups that do not adjust for factors associated with treatment choice may be biased. Propensity score technique offers a highly practical approach to address such bias [283]. Here, the probability of each participant being in the treatment arm (i.e., the propensity score), is estimated. Participants are sorted by their propensity scores; the sample is divided into strata based on estimated scores, the treatment effect within each stratum estimated and overall estimate computed by aggregating across strata in a weighted analysis. When the model for predicting treatment status includes all relevant covariates, within strata treatment groups will be balanced on all predictors and the overall comparison of treatment arms will have substantially lower bias. We will use a model relating PCa treatment (RP, RALP, EBRT, PT, BT or AS) to baseline factors [283-284]. To study the extent to which treatment groups are now matched, we will compare t-statistics for these covariates before and after adjusting for propensity score. This will be done separately for intervention group and usual care controls. **Instrumental variable analysis:** Another limitation of observational research is the strong potential for confounding bias, due to differences in comparison groups that are not reflected in the data (i.e., unobserved bias). The instrumental variable (IV) approach is useful in reducing this bias. This technique uses one or more observable factors that influence outcome only indirectly (the IV). This allows one to mimic randomization with different likelihoods of receiving a particular treatment [227, 285-291]. Physicians play an important role in patients treatment choice- a majority of the PCa patients report that their physicians recommendation was the most important factor in their treatment choice [11-12, 37-46, 51, 55-56, 60-64]. We will use specialty of the first physician (urologist, urologic oncologist, oncologist, radiation oncologist) who the patient saw during PCa diagnosis as an IV. We will explore other potential IVs, such as absolute distance between patients residence to the hospital where they will receive care (Hospital of University of Pennsylvania, Presbyterian Medical Center, PVAMC, Pennsylvania Hospital, or Fox-Chase Cancer Center). Validity of the IV(s) is assessed as following. First, we will use Pearsons correlation coefficient to examine the correlation between IV, primary exposure (treatment) and outcomes. We will then perform a partial F-test using a linear regression where treatment group is regressed on physician specialty along with patient attributes. For a valid IV, test statistic should be very high (e.g., physician specialty will strongly predict treatment after adjusting for covariates). Next, we will perform a partial F-test using a linear probability model in which HRQoL outcomes are regressed on specialty and patient demographic and clinical variables. For an IV to be valid, this test statistic should be very low. Finally, we will compare observable attributes across patient groups cared for by different physician specialty (initial). For the IV be valid, these groups should have comparable observable attributes. **Phase 1 Focus group analysis-development of conjoint task instrument:** The goal of focus groups is to identify attributes of PCa treatment that are most salient to localized PCa patients. This process includes following steps: (1) identifying and defining attributes; (2) assigning attribute levels; and (3) creating scenarios and choice sets. Attributes will be defined based on input from patient focus groups, literature, our prior research, and prior physician focus group. Once an attribute and its extreme values are defined, we will assign them appropriate levels. A large number of possible combinations of attributes and levels will preclude

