patients in decision (measured using CPS) using multi-nominal regression model to adjust for observed covariates. Then we will examine if these associations vary across intervention and usual care control groups. We then will repeat the model with other independent variables (decision conflict and trust). Next, we will test the association denoted by path c (direct effect of DCS, CPS, and trust on outcomes). For continuous outcomes (HRQoL, AUA-SI, MAX-PC, CES-D, SWD, and PSQ-18), we will compute area under the curve (AUC) for each measure for each patient. We will analyze AUC summaries with univariate linear models. In our main analysis we will analyze the series of functional status measures using linear mixed models that predict the outcome from time, independent variables and their interaction. We will repeat the analyses described for path c, this time by including treatment received in the models. We will test if the observed effects of DCS, CPS or trust on outcomes will be weaker after controlling for treatment. These analyses will be performed within and between groups (intervention and usual care controls). Specific Aim 3: Hypothesis: Prostate cancer patients in the intervention group undergoing conjoint analysis-value clarification exhibit improved treatment choice, satisfaction with decision, lower regrets, and improved objective and subjective outcomes. Analysis for Specific Aim 3 uses intent-to-treat approach: all randomized participants will be included regardless of whether they drop out of the intervention or study. Analysis will involve comparison of the primary outcomes between intervention and usual care control groups. Improved treatment choice is operationalized as the likelihood of low-risk PCa patients receiving active surveillance than active treatment, and will be compared between intervention and usual care control group. To allow for different trajectories of the outcome measures and to afford flexibility in making contrasts within participants over time and across participants, while simultaneously controlling for potential confounders, we propose the participant-specific or mixed effects linear model, in which the mean outcome depends on fixed covariates and random effects. The primary fixed effects will be indicators for intervention group and hospital. We will also stratify the analysis by type of treatment. The random effects represent the unobserved factors that lead to variation of the individual participants outcome. Random intercepts for each participant permit modeling of natural variation across participants at baseline. In addition, random slopes or random effects for the trajectory of each participant over time, allow for variation of each participant about a mean, overall trajectory across all participants. Although less robust to model misspecification, the mixed effects paradigm offers special flexibility in longitudinal data when exposures vary over time and when dropout and missed visits lead to unbalanced groups. The target of inference is the participant-specific response to treatment over time. At each time point of interest, we will estimate from the fitted model the difference from baseline in outcome for the treatment and control groups and test the difference between these differences. Both univariate and multivariate results will be reported in terms of Wald test, point estimates, and 95% confidence intervals. Specific Aim 4: Hypothesis 4: Prostate cancer patients whose treatment is more concordant with their values markers will experience improved subjective and objective outcomes. This specific aim s for intervention group only. We will analyze the association of the concordance between stated individual preferences and actual treatment received with objective (PCa recurrence and complications), subjective (HRQoL, psychological wellbeing, SWD, and satisfaction with care) outcomes, across treatment groups, adjusting for covariates. Association between the value markers (profiles) and measures of outcomes and personal and clinical characteristics: The value markers will be studied for their relationship with socio-demographic and clinical characteristics. We will also assess the association of value markers with outcomes. We will perform logistic regression with outcomes as the dependent variable and dummy variables for the utility-based profiles obtained earlier as independent variables. We will perform this evaluation with and without adjusting for patient attributes in the logistic model. For each case (adjusting and not adjusting for patient attributes), the evaluation of association between these profiles and outcomes will be based on a likelihood ratio test of the set of odds ratios corresponding to the dummy variables of the profiles. Additionally, we will perform a sequence of pair wise tests of comparisons of the profiles in terms of the proportion of type of treatment received based on the Holms multiple comparisons approach. This procedure is hierarchical in that it will identify the utility-based profile at the start of the process before making other comparisons, thus protecting the Type I error from additional comparisons. Specifically, Holms approach tests each pair-wise comparison in ascending order of p-values. Successively larger p-values have less rigorous alpha. The sequential Holm tests terminate after the first non-significant comparison so no subsequent comparison is significance. Concordance and its assessment: Understanding and respect for the patients preference and values is the main aspect of concordance [69, 73]. Thus a first step in concordance involves the physician extracting and understanding the patients view, followed by an agreement between the physician and patient regarding a management plan that integrates their views. There exist many definitions of concordance. For the purpose of this study, we operationalized concordance as agreement between a patients value markers and the attributes (or characteristics) of the treatment that

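### No baseline outcome score is named as a covariate for the non-randomised analyses, so in the Aim 2 AUC and follow-up-level models an association already present at baseline can pass for an effect

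*Combined protocol and SAP*

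**What the plan says.** **Covariates.** D.2.4.4 (Potential confounding variables), repeated under the primary outcome heading, names disease stage, grade, histology, Gleason score and the Elixhauser index. It then adds possible demographic covariates: "We will gather baseline data on patient age, income, education, health insurance, occupation, marital status, smoking status, height, weight and family history of PCa". No quality-of-life, symptom, mood or satisfaction score appears.

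**Baseline data.** The Procedures section has these instruments completed before treatment starts: "SF-36, EPIC, AUA-SI, regret scale, CES-D, MAX-PC, SWD, PSQ-18, CPS, DCS and trust scale". The outcome scales are repeated at 3, 6, 12 and 24 months.

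**Propensity model.** The Analysis Plan says "We will use a model relating PCa treatment (RP, RALP, EBRT, PT, BT or AS) to baseline factors", with no list of those factors. It is applied separately in the intervention and control groups.

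**Aim 2, path c.** For the direct effect of decision conflict, role preference and trust on outcomes, an area under the curve is computed per patient: "We will analyze AUC summaries with univariate linear models". The main analysis is a linear mixed model with time, the predictor and their interaction. Neither description mentions the baseline value of the outcome, whether the baseline visit counts as an outcome visit, or which coefficient is tested.

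**The concern.** The protocol's premise is that men choose treatment by weighing urinary, sexual, bowel and general health effects. Pre-treatment function is then a plausible cause of treatment choice, and it also predicts the same score later. A propensity model built only from the D.2.4.4 variables need not balance it.

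In Aim 2 the predictors and the baseline outcomes are measured in the same pre-treatment period. A man who is distressed at diagnosis may report more decision conflict, less trust, lower mood and worse quality of life all at once. An AUC or follow-up-level model without the baseline score carries that association forward and reports it as a direct effect of decision conflict or trust on outcome. At stake is whether a positive path c result means anything beyond correlation at diagnosis.

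**Working it through.** **Inputs from the protocol (Accrual section).** "We assume 80% power"; two-sided alpha 0.05; "We assume a conservative intra-class correlation of 0.3 and 4 follow-up measures per subject"; 10% dropout; 360 per arm, 60 per arm within a treatment type. On spread: "the standard deviations for the PCI and SF-36 scales in samples of men with PCa mostly range from 8 to 14".

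**Inputs assumed, because the documents do not give them.** Residual baseline gap d = 0.25 to 0.5 SD; baseline-to-follow-up correlation r = 0.3 (the protocol's intra-class correlation) to 0.6; correlation of decision conflict with the baseline score r_b = 0.2 to 0.3; the same correlation r between all visits.

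**1. The protocol's own figures.** Detectable difference = (1.96 + 0.84) × SD × √[(2/n) × (1 + 3 × 0.3)/4], with n after dropout.

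| n per group | SD 8 | SD 14 | Stated |
|---|---|---|---|
| 324 | 1.21 | 2.12 | 1.2 |
| 54 | 2.97 | 5.20 | 3.0 |

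The stated figures reproduce at SD 8 only. A bias computed at SD 14 must therefore be set against 5.2, not 3.0.

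**2. Aim 2, no later effect.** Induced correlation with the four-visit mean = r_b × r / √[(1 + 3r)/4]. Rejection rate by Fisher z with n = 720 × 0.9 = 648.

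| r_b | r | Induced correlation | z | Rejection at 0.05 |
|---|---|---|---|---|
| 0.2 | 0.3 | 0.087 | 2.22 | 60% |
| 0.3 | 0.3 | 0.131 | 3.34 | 92% |
| 0.2 | 0.6 | 0.143 | 3.67 | 96% |
| 0.3 | 0.6 | 0.215 | 5.55 | >99% |

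The four-visit mean stands in for the AUC. If the AUC also includes the baseline visit, the trapezoid rule over 0, 3, 6, 12 and 24 months gives that visit a weight of 1.5/24 = 0.0625, which adds to the problem.

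**3. Treatment comparisons, no true effect.** If the gap arises from selection on the baseline score, the bias is r × d × SD in the follow-up score and −(1 − r) × d × SD in the change score.

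| SD | Follow-up score | Change score | Detectable, n = 54 |
|---|---|---|---|
| 8 | 0.6 to 2.4 | −0.8 to −2.8 | 3.0 |
| 14 | 1.05 to 4.2 | −1.4 to −4.9 | 5.2 |

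**4. Which adjustment works.** Simulation with 4,000 runs per setting: 54 per group, SD 8, correlation 0.3, baseline gap 5 points, no true effect.

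| Analysis | Selection on baseline score: estimate, rejection | Stable-trait gap: estimate, rejection |
|---|---|---|
| AUC including baseline | 1.7, 36% | 5.0, >99% |
| Follow-up mean | 1.5, 29% | 5.0, >99% |
| Follow-up mean with baseline covariate | 0.0, 6% | 3.5, 94% |
| Change from baseline | −3.5, 66% | 0.0, 5% |

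Neither adjustment is right in both settings.

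**The case against.** **The list is not closed.** A reader might infer that the plan excludes baseline scores from the propensity model. It does not say so. D.2.4.4 is headed as potential confounders, its demographics are possible covariates, and the Analysis Plan says balance depends on including all relevant covariates. The predictors are unspecified, not excluded. This stands, and it is the reason to itemise them.

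**Baseline enters elsewhere.** It would be wrong to say that every Aim 2 and Aim 4 analysis ignores baseline. The Aim 2 main model has a predictor-by-time interaction, and a constant offset falls in the main effect. Aim 4's primary comparisons are with baseline. This narrows the point to the AUC models and any model of follow-up level. The interaction is not immune: if the association belongs to the baseline state, it falls from 0.2–0.3 at baseline to r_b × r = 0.06–0.18 afterwards. That fading can load on the interaction if baseline is an outcome visit.

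**Multiplicity.** The 60% to 100% range uses 0.05, while the plan foresees a Bonferroni correction over an undefined family. With ten tests, an assumed number, the lowest entry falls from 60% to about 28%. That is still far above nominal.

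**Comparison with 3.0 points.** It is tempting to say that the treatment-comparison bias exceeds the detectable difference. With SDs matched it does not: 2.4 against 3.0, and 4.2 against 5.2. The 3.0 points also refer to the two randomised arms within a treatment type, not to one treatment against another.

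**Unobserved bias.** An instrumental-variable analysis is also planned, but it concerns treatment received and gives no baseline adjustment to path c.

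**Conclusion.** The omission is real. No section names a baseline outcome score as a covariate, and the Aim 2 AUC models state no baseline adjustment. Followed as written, a purely cross-sectional association at baseline would be significant in about 60% to 100% of null trials, given r_b of 0.2 to 0.3, r of 0.3 to 0.6, 648 men and alpha 0.05 before Bonferroni. In treatment comparisons the bias is 0.6 to 2.4 points (SD 8) or 1.1 to 4.2 points (SD 14) for a residual gap of 0.25 to 0.5 SD. That is below the matched detectable differences but not negligible beside them. All of these sizes rest on assumed gaps and correlations; with no residual gap or baseline association there is no bias of this kind.

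Two further readings should be resisted. Change scores are not wrong in general: they are unbiased if the gap is a stable trait, a case in which covariate adjustment removes only part of the bias. And the randomised Aim 3 comparison is not affected: its arms are formed by randomisation and it already tests differences from baseline.

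**What to change.** 1. **Aim 2, path c.** Compute the AUC over the follow-up visits only, and adjust the AUC and level models for the baseline score of the outcome analysed. In the mixed model, do not also use baseline as an outcome visit, and state which coefficient is tested.
2. **D.2.4.4 and the propensity model.** Itemise the predictors and include a short set of baseline scores, for example the EPIC domains, AUA-SI, SF-36 summary scores, CES-D and MAX-PC.
3. **Sensitivity analysis.** Report change from baseline alongside, and say that the two analyses guard against different mechanisms. Disagreement between them is a reason for caution about the result.

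**Cost.** No new data, visits or patients are needed. The price is model size. The propensity adjustment is done separately by arm, with about 60 men per treatment. If the model is multinomial (its form is not stated), each score adds five coefficients. Four EPIC domains, AUA-SI, eight SF-36 domains, CES-D and MAX-PC make 15 scores, so 15 × 5 = 75 coefficients for 360 men. With two SF-36 summary scores in place of the eight domains (an assumed number), it is 9 × 5 = 45. The set should be kept short and fixed before outcome data are examined.
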